6.2.3 Follow-up period and trial completion

For patients that complete the treatment period, a Follow up Visit will be conducted 28 days after the EoT visit based on the half-life of the trial medication.

If patient discontinues the trial early, the Termination of Trial Medication eCRF page must be completed and a Follow-up Visit should be completed 28 days after eEoT Visit.

AEs which have not recovered at Follow-up Visit should be followed up until they are resolved, have been assessed as “chronic” or “stable”, or no further information can be obtained.

All patients with Hb drop below 100 g/L (10 g/dL) or absolute decrease >20 g/L (2 g/dL) since baseline (Visit 2) will need to be followed up post-end of study until value returns to baseline/normal value, or resolution (per investigator's judgment).

7. STATISTICAL METHODS AND DETERMINATION OF SAMPLE SIZE

7.1 STATISTICAL DESIGN - MODEL

This is a randomized, double-blind, placebo-controlled, parallel group trial with a 12-week Treatment Period. The primary objective of this trial is to provide PoC data by assessing the effect on cognition of oral once daily administration of BI 425809 given for 12 weeks in patients with schizophrenia on stable antipsychotic treatment and adjunctive CCT.

The primary endpoint is change from baseline in neurocognitive function as measured by the neurocognitive composite score of the MCCB after 12 weeks of treatment, which is the overall MCCB composite score excluding the Social Cognition domain score. A detailed description of the model utilized is provided in [Section 7.3.1](#).

For a description of the secondary endpoints, please refer to [Section 2.1.3](#).

7.2 NULL AND ALTERNATIVE HYPOTHESES

This trial is designed to assess the effects of BI 425809 with adjunctive CCT and placebo with adjunctive CCT on cognition in patients with schizophrenia on stable antipsychotic treatment.

There will be no formal hypothesis testing performed. Inference concerning the efficacy of BI425809 with adjunctive CCT will be accessed based on the estimated mean difference(s) between the treatment and placebo arm on the MCCB neurocognitive composite score change from baseline after 12 weeks of treatment, as well as other efficacy endpoints.

7.3 PLANNED ANALYSES

The following patient analysis sets are defined for this trial:

- Randomized Set (RS): includes all patients who signed informed consent and were randomized to receive either BI 425809 + CCT or placebo + CCT.
- Treated Set (TS): includes all patients in RS who were treated with at least one dose of the trial regimen (including both drug and CCT). Patients in TS are analyzed under the actual trial regimen received at randomization. The TS is used for safety analyses as well as demographics and baseline characteristics and treatment regimen exposure.
- Full Analysis Set (FAS): includes all patients in treated set who had non-missing baseline and at least one non-missing post-baseline on-treatment measurement on the primary efficacy endpoint. The FAS is used for efficacy analyses and patients will be analyzed as randomized.

- 

Data from patients who were screened but not randomised will be listed but not included in any inferential statistics.

The list of IPDs is described in the study TSAP.

Handling of randomised patients who received the wrong treatment will be specified in the TSAP.

Baseline

The baseline for MCCB neurocognitive composite score, and all other efficacy-related endpoints is defined as the measurement taken at randomization (Visit 2), and prior to the first administration of the study drug.

7.3.1 Primary endpoint analyses

The primary analysis of the primary efficacy endpoint will be performed on FAS. The Restricted Maximum Likelihood (REML)-based MMRM model will be fitted for the change from baseline in the MCCB neurocognitive composite score after 12 weeks of treatment. The model will include the continuous baseline MCCB neurocognitive composite score, and change in the MCCB neurocognitive composite score from screening to baseline as covariates, treatment (BI 425809 + CCT vs. placebo + CCT), age (≤ 40 vs. > 40) and visit as factors, as well as the treatment-by-visit and baseline-by-visit interactions. Patient will be treated as random effect. The unstructured variance-covariance structure will be used to model the within-patient errors. The Kenward-Roger approximation will be used to estimate the denominator degrees of freedom. Analyses will be implemented using SAS PROC MIXED. The primary treatment comparisons will be the contrasts between treatment groups (BI 425809 + CCT vs. placebo drug + CCT) at Week 12. Estimated least squares mean difference between treatment arms will be provided.

For the definition of MCCB neurocognitive composite score, please refer to [Section 7.1](#).

7.3.2 Secondary endpoint analyses

A specification of secondary endpoints is provided in [Section 2.1.3](#).

The analyses of efficacy-related secondary endpoints will be performed in FAS. The same model utilized for the primary endpoint will be fitted for change from baseline in the overall MCCB composite score. For change from baseline in PANSS total score after 12 weeks of treatment, an MMRM model that includes treatment, age and visit as factors, the corresponding baseline value as a covariate, as well as treatment-by-visit and baseline-by-visit interactions will be fitted. For change from baseline in SCoRS score after 12 weeks of treatment, an ANCOVA model that includes treatment and age as factors, and its corresponding score at baseline as a covariate will be fitted. The adjusted mean values as well as the treatment group contrasts at week 12 will be presented together with the 95% confidence intervals (CI). All p-values will be considered descriptive.

For the percentage of patients with (S)AEs (including clinically relevant abnormalities of physical examination, vital signs, ECG and laboratory tests), comparison will be made for (BI 424809 + CCT) group vs. (placebo + CCT) group on TS together with descriptive statistics.

For other secondary endpoints, only descriptive statistics and exploratory analyses will be provided.

Other analyses may be considered if deemed necessary and the details will be provided in the TSAP.

7.3.4 Safety analyses

AEs will be coded using the Medical Dictionary for Drug Regulatory Activities (MedDRA). Standard BI summary tables and listings will be produced. All AEs with an onset between start of treatment and the end of the REP, a period of 11 days after the last dose of trial medication, will be assigned to the on Treatment Period for evaluation.

All treated patients will be included in the safety analysis. In general, safety analyses will be descriptive in nature and will be based on BI standards. No hypothesis testing is planned.

Statistical analysis and reporting of AEs will concentrate on treatment-emergent adverse events, i.e. all AEs occurring between start of treatment and end of the REP. AEs that start

before first drug intake and deteriorate under treatment will also be considered as ‘treatment-emergent’.

Frequency, severity, and causal relationship of AEs will be tabulated by system organ class and preferred term after coding according to the current version of the MedDRA at the database lock.

Laboratory data will be analysed both quantitatively as well as qualitatively. The latter will be done via comparison of laboratory data to their reference ranges. Values outside the reference range as well as values defined as clinically relevant will be summarised. Treatment groups will be compared descriptively with regard to distribution parameters as well as with regard to frequency and percentage of patients with abnormal values or clinically relevant abnormal values.

Vital signs, physical examinations, or other safety-relevant data observed at screening (Visit 1), baseline (Visit 2), during the course of the trial and at the end-of-trial evaluation will be assessed with regard to possible changes compared to findings before start of treatment.

7.5 HANDLING OF MISSING DATA

Every effort will be made to collect complete data at the pre-planned time points. Handling of missing data in MCCB tests will follow the MCCB Manual (available in the ISF). In general, for completely missing visit missing data will not be imputed and will be handled through the MMRM under the “missing at random” assumption. BI standards will be used for missing data in AE, safety lab, [REDACTED]. The missing data handling rules will be further specified in details in the TSAP.

7.6 RANDOMIZATION

Eligible patients will be stratified by age (age 18-40 and age 41-50) and will be randomized with 1:1 ratio to the BI 425809 10 mg + CCT and placebo + CCT arms. The randomization will be implemented in blocks to achieve balanced allocation to each of the two treatment arms. The block size will be documented in the clinical trial report (CTR).

The randomization will be conducted via an IRT. BI will arrange for the randomization and the packaging and labelling of trial medication. The randomization list will be generated by a validated system, which utilizes a pseudo-random number generator to make the resulting treatment sequence both reproducible and non-predictable. Access to the randomization codes will be controlled and documented.

The investigator will inform the sponsor immediately of any urgent safety measures taken to protect the trial patients against any immediate hazard, as well as of any serious breaches of the protocol or of ICH-GCP.

The Boehringer Ingelheim transparency and publication policy can be found on the following web page: trials.boehringer-ingelheim.com. The rights of the investigator and of the sponsor with regard to publication of the results of this trial are described in the investigator contract. As a rule, no trial results should be published prior to finalization of the CTR.

The certificate of insurance cover is made available to the investigator and the patients, and is stored in the ISF.

8.1 DATA QUALITY ASSURANCE

A risk-based approach is used for trial quality management. It is initiated by the assessment of critical data and processes for trial subject protection and reliability of the results as well as identification and assessment of associated risks. An Integrated Quality and Risk Management Plan documents the rationale and strategies for risk management during trial conduct including monitoring approaches, vendor management and other processes focusing on areas of greatest risk.

Continuous risk review and assessment may lead to adjustments in trial conduct, trial design or monitoring approaches.

A quality assurance audit/inspection of this trial may be conducted by the sponsor, sponsor's designees, or by IRB / IEC or by regulatory authorities. The quality assurance auditor will have access to all medical records, the investigator's trial-related files and correspondence, and the informed consent documentation of this clinical trial.

8.2 TRIAL APPROVAL, PATIENT INFORMATION, INFORMED CONSENT

This trial will be initiated only after all required legal documentation has been reviewed and approved by the respective IRB / IEC and Competent Authority (CA) according to national and international regulations. The same applies for the implementation of changes introduced by amendments.

Prior to patient participation in the trial, written informed consent must be obtained from each patient (or the patient's legally accepted representative) according to ICH-GCP and to the regulatory and legal requirements of the participating country. Each signature must be personally dated by each signatory and the informed consent and any additional patient-information form retained by the investigator as part of the trial records. A signed copy of the informed consent and any additional patient information must be given to each patient or the patient's legally accepted representative.

Re-consenting may become necessary when new relevant information becomes available and should be conducted according to the sponsor's instructions.

If study conduct may need to be adjusted during the COVID-19 pandemic (see [Section 6.2](#) and [Section 10.5](#)), the patient must be made aware of any modifications and provide their agreement to the modifications prior to them being implemented.

The consent and re-consenting process should be properly documented in the source documentation.

8.3 RECORDS

CRFs for individual patients will be provided by the sponsor. See [Section 4.1.5.2](#) for rules about emergency code breaks. For drug accountability, refer to [Section 4.1.8](#).

8.3.1 Source documents

In accordance with regulatory requirements, the investigator should prepare and maintain adequate and accurate source documents and trial records that include all observations and other data pertinent to the investigation on each trial patient. Source data as well as reported data should follow the "ALCOA principles" and be attributable, legible, contemporaneous, original and accurate. Changes to the data should be traceable (audit trail).

Data reported on the eCRF must be consistent with the source data or the discrepancies must be explained.

The current medical history of the patient may not be sufficient to confirm eligibility for the trial and the investigator may need to request previous medical histories and evidence of any diagnostic tests. If medical records cannot be obtained prior to randomization, a phone call with the treating physician(s) detailing eligibility information must be conducted and documented, and the documentation filed with the subject's source records. If medical records cannot be obtained and a phone call with the treating physician(s) cannot be conducted, the CTM or CTL should be contacted for further discussion.

8.3.2 Direct access to source data and documents

The sponsor will monitor the conduct of the trial by regular on-site monitoring visits and in-house data quality review. The frequency of site monitoring will be determined by assessing all characteristics of the trial, including its nature, objective, methodology and the degree of any deviations of the intervention from normal clinical practice.

The investigator /institution will allow site trial-related monitoring, audits, IRB / IEC review and regulatory inspections. Direct access must be provided to the eCRF and all source documents/data, including progress notes, copies of laboratory and medical test results, which must be available at all times for review by the CRA, auditor and regulatory inspector (e.g. United States Food and Drug Administration). They may review all eCRFs and informed consents. The accuracy of the data will be verified by direct comparison with the source documents described in [Section 8.3.1](#). The sponsor will also monitor compliance with the protocol and ICH-GCP.

8.3.3 Storage period of records

Trial site(s)

The trial site(s) must retain the source and essential documents (including ISF) according to contract or the local requirements valid at the time of the end of the trial (whatever is longer).

Sponsor

The sponsor must retain the essential documents according to the sponsor's SOPs.

8.4 EXPEDITED REPORTING OF ADVERSE EVENTS

BI is responsible to fulfil their legal and regulatory reporting obligation in accordance with regulatory requirements.

8.5 STATEMENT OF CONFIDENTIALITY AND PATIENT PRIVACY

Individual patient data obtained as a result of this trial is considered confidential and disclosure to third parties is prohibited with the exceptions noted below. Patient privacy will be ensured by using patient identification code numbers.

Data protection and data security measures are implemented for the collection, storage and processing of patient data in accordance with the principles 6 and 12 of the World Health Organization Good Clinical Practices handbook and the EU General Data Protection Regulation.

Personalised treatment data may be given to the patient's personal physician or to other appropriate medical personnel responsible for the patient's welfare. Data generated at the site as a result of the trial need to be available for inspection on request by the participating physicians, the sponsor's representatives, by the IRB / IEC and the regulatory authorities.

8.5.1 Collection, storage and future use of biological samples and corresponding data

Not applicable

8.6 TRIAL MILESTONES

The **start of the trial** is defined as the date when the first patient in the whole trial signs informed consent.

The **end of the trial** is defined as the date of the last visit of the last patient in the whole trial ("Last Patient Completed").

The "**Last Patient Last Treatment**" (LPLT) date is defined as the date on which the last patient in the whole trial is administered the last dose of trial treatment (as scheduled per protocol or prematurely). Individual investigators will be notified of SUSARs occurring with the trial medication until 30 days after LPLT at their site.

Early termination of the trial is defined as the premature termination of the trial due to any reason before the end of the trial as specified in this protocol.

Temporary halt of the trial is defined as any unplanned interruption of the trial by the sponsor with the intention to resume it.

Suspension of the trial is defined as an interruption of the trial based on a Health Authority request.

The IEC / CA in each participating EU member state will be notified about the trial milestones according to the respective laws.

A final report of the clinical trial data will be written only after all patients have completed the trial in all countries (EU or non-EU) to incorporate and consider all data in the report. The sponsor will submit to the EU database a summary of the final trial results within one year from the end of a clinical trial as a whole, regardless of the country of the last patient (EU or non-EU).

8.7 ADMINISTRATIVE STRUCTURE OF THE TRIAL

The trial is sponsored by Boehringer Ingelheim (BI).

A Coordinating Investigator is responsible to coordinate investigators at the different sites participating in this trial. Tasks and responsibilities are defined in a contract.

Relevant documentation on the participating (Principal) Investigators (e.g. their curricula vitae) will be filed in the ISF.

The investigators will have access to the BI clinical trial portal Clinergize to access documents provided by the sponsor.

BI has appointed a CTL, responsible for coordinating all required activities, in order to

- manage the trial in accordance with applicable regulations and internal SOPs,
- direct the clinical trial team in the preparation, conduct, and reporting of the trial,
- ensure appropriate training and information of CTMs, CRAs, and investigators of participating countries.

The organisation of the trial in the participating countries will be performed by the respective local or regional BI-organisation (Operating Unit, OPU) in accordance with applicable regulations and BI SOPs, or by a Contract Research Organisation (CRO) with which the responsibilities and tasks will have been agreed and a written contract filed before initiation of the clinical trial.

Data Management and Statistical Evaluation will be done by BI according to BI SOPs.

Tasks and functions assigned in order to organise, manage, and evaluate the trial are defined according to BI SOPs. A list of responsible persons and relevant local information can be found in the ISF.

A central laboratory service, a central images service for ECG, an IRT vendor and a vendor for delivery of the CCT exercises will be used in this trial. Details will be provided in the Central Laboratory Manual, ECG Manual, IRT Manual and CCT Manual, respectively, available in the ISF.

10. APPENDICES

10.1 INSTRUCTIONS FOR USE

Further instructions for use of the CCT program will be described in the CCT Manual available in the ISF.

Additionally, instructions for use of the central laboratory service, central images service for ECG and IRT system will be described in the Central Laboratory Manual, ECG Manual and IRT Manual, respectively, available in the ISF.

10.5 POTENTIAL MODIFICATION OF TRIAL CONDUCT IN CASE OF RESTRICTIONS DUE TO COVID-19

As mentioned in [Section 6.2](#), in case of any new restrictions during the COVID-19 pandemic and for patients already in the study, study conduct may need to be adjusted based on the investigator's discretion (and agreed with the sponsor). The following contingency measures have been introduced to ensure patient safety and appropriate trial continuation based on a thorough benefit-risk assessment of treatment continuation versus early discontinuation, to be judged by the investigator on an individual patient level whereby patient safety always needs to be at the centre of decision-making (see [Section 1.4](#)).

In exceptional cases, when it is impossible to conduct the visits at the trial site, visits may be performed at the patient's home or remotely (via telephone and/or internet based means of communication). The visits may also be performed as a combination of home and remote visits. Based on a thorough benefit-risk assessment (see [Section 1.4](#)), the visit procedures may be adjusted for the purpose of particular visits, whereby critical safety measures will remain in place. All home/remote visits need to be discussed with and approved by the sponsor.

Local regulatory and legal requirements of the participating country need to be respected for all modifications. Patients need to be informed about the modifications and agree to them before implementation (see [Section 8.2](#)).

Under these circumstances, the below modifications can be considered.

Remote visit

If a patient is not able to come to the site for an in-clinic trial visit, a remote visit (by phone) should be performed instead and all assessments that can be done by phone performed.

The following study data may be collected/reported during phone contacts: Adverse events, concomitant therapies, C-SSRS, birth control check (for women of childbearing potential), SCoRS and PANSS, [REDACTED], and study medication and CCT compliance checks. Patients can report and/or send photos of study medication kit used to their site staff, if needed and possible.

Additional guidance for assessing specific symptoms as part of adverse event check during phone contacts is available to investigators and should be followed.

MCCB cannot be done via phone, but in certain situations it may be possible to complete some MCCB sub-tests (enough to derive a composite score) via videoconference between the rater and the patient, if agreed with sponsor. If necessary during COVID-19 pandemic, based on the REP for BI 425809 (as defined in [Section 1.2](#)), Visit 6/(e)EoT Visit may be delayed up to 10 days following the last dose of trial medication, in case this helps to facilitate an in-clinic trial visit with MCCB assessment.

Safety and other laboratory tests, vital signs, ECG

If blood sampling for central lab at the trial site is not possible, safety lab analyses can be performed at a local laboratory. The results of the lab tests must be transferred to the investigator who ensures medical review and proper documentation in the eCRF.

Recommended minimum safety lab parameters are: Hematology, Urea (BUN), Creatinine, eGFR, liver enzymes, pregnancy test (for WOCBP).

If home visits are possible, some assessments can be done at the patient's home (e.g. collection of blood and urine samples to be sent to the central lab, vital signs).

Direct-to-patient shipment of trial medication

If a patient is not able to come to Visit 3, Visit 4 or Visit 5 as planned but the investigator considers it favorable and safe for the patient to continue on trial medication, the trial medication can be shipped from site directly to the patient (if acceptable according to local laws and regulations). Such shipments require the use of a sponsor approved courier to the patient's home. Investigators should conduct phone visits first to discuss adverse events, concomitant therapies, C-SSRS, birth control check, and assess study medication and CCT compliance. If possible and as per investigator's clinical judgement, safety laboratory tests should be done at a local laboratory.

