Cancers of new histology and exacerbations of existing cancer must be classified as a serious event regardless of the time since discontinuation of the drug and must be reported as described in [Section 5.2.6.2](#), sub-sections “AE Collection” and “AE reporting to sponsor and timelines”.

In accordance with the European Medicines Agency initiative on Important Medical Events, Boehringer Ingelheim has set up a list of further AEs, which by their nature, can always be considered to be “serious” even though they may not have met the criteria of an SAE as defined above.

The latest list of “Always Serious AEs” can be found in the eDC system. These events should always be reported as SAEs as described above.

Adverse events of special interest (AESIs)

The term AESI relates to any specific AE that has been identified at the project level as being of particular concern for prospective safety monitoring and safety assessment within this trial, e.g. the potential for AEs based on knowledge from other compounds in the same class. AESIs need to be reported to the sponsor’s Pharmacovigilance Department within the same timeframe that applies to SAEs, please see above.

The following are considered as AESIs:

Hepatic injury

A hepatic injury is defined by the following alterations of hepatic laboratory parameters:

- an elevation of AST (aspartate transaminase) and/or ALT (alanine aminotransferase) ≥ 3 fold ULN combined with an elevation of total bilirubin ≥ 2 fold ULN measured in the same blood draw sample, or
- aminotransferase (ALT, and/or AST) elevations ≥ 10 fold ULN

These lab findings constitute a hepatic injury alert and the patients showing these lab abnormalities need to be followed up according to the “DILI checklist” provided in the eDC system.

In case of clinical symptoms of hepatic injury (icterus, unexplained encephalopathy, unexplained coagulopathy, right upper quadrant abdominal pain, etc.) without lab results (ALT, AST, total bilirubin) available, the investigator should make sure these parameters are analysed, if necessary in an unscheduled blood test. Should the results meet the criteria of hepatic injury alert, the procedures described in the DILI checklist should be followed.

Intensity (severity) of AEs

The intensity (severity) of the AE should be judged based on the following:

Mild:	Awareness of sign(s) or symptom(s) that is/are easily tolerated
Moderate:	Sufficient discomfort to cause interference with usual activity

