#### Adverse events of special interest (AESIs)

[figure not shown]
As defined in CTP Section 5.2.6.1, AESI includes hepatic injury defined by the following alterations of hepatic laboratory parameters:

- an elevation of AST (aspartate transaminase) and/or ALT (alanine aminotransferase) >3-fold ULN combined with an elevation of total bilirubin >2-fold ULN measured in the same blood draw sample, or
- aminotransferase (ALT, and/or AST) elevations  $\geq 10$ -fold ULN.

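### The minimum local-laboratory panel for COVID-19 restrictions does not name total bilirubin, so a draw limited to it cannot be assessed against the combined hepatic-injury criterion of the only listed AESI

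*Protocol*

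**What the plan says.** **Local testing.** Under COVID-19 restrictions, Protocol Section 10.5 says that "safety lab analyses can be performed at a local laboratory" if sampling for the central laboratory at the site is not possible. It then gives the list: "Recommended minimum safety lab parameters are: Hematology, Urea (BUN), Creatinine, eGFR, liver enzymes, pregnancy test (for WOCBP". The same section promises that visit procedures may be adjusted, "whereby critical safety measures will remain in place".

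**The AESI.** Protocol Section 5.2.6.1 opens its list with "The following are considered as AESIs" and names one item, hepatic injury. This is met in either of two ways:

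- AST and/or ALT at or above 3-fold ULN, together with "total bilirubin ≥ 2 fold ULN measured in the same blood draw sample"; or
- "aminotransferase (ALT, and/or AST) elevations" at or above 10-fold ULN, with no bilirubin condition.

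Meeting either one is a hepatic injury alert. It brings AESI reporting on the SAE timeline and follow-up by the DILI checklist.

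**The standard panel.** Protocol Table 5.2.3: 1 lists total bilirubin as its own chemistry test, apart from AST, ALT, alkaline phosphatase and GGT.

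**The SAP.** Section 7.8.1 says it takes the AESI definition from Protocol Section 5.2.6.1. It uses strict inequalities for the combined criterion (AST/ALT above 3-fold, and "total bilirubin >2-fold ULN measured in the same blood draw sample") but keeps at-or-above for the 10-fold criterion.

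**The concern.** A minimum panel tells a site what is enough. Here a site can do exactly what Section 10.5 recommends and still hold a sample that cannot be judged against one of the two criteria for the trial's only listed AESI. Bilirubin is not an enzyme, and the protocol's own laboratory table treats it as a separate test, so the term liver enzymes does not literally cover it.

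This fits poorly with Section 1.4, which calls for timely detection of liver laboratory changes and points to the AESI section, and with the assurance in Section 10.5 about critical safety measures. At stake are the speed and completeness of hepatic alerts, and with them the AESI table planned in SAP Section 7.8.1, which could undercount.

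**Working it through.** No arithmetic is needed; the check compares the analytes available with the analytes required.

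**Step 1: panel against criteria.**

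| Criterion (Protocol 5.2.6.1) | Needs | In the 10.5 minimum? | Assessable on a minimum-panel draw? |
|---|---|---|---|
| Combined: AST/ALT ≥3-fold and total bilirubin ≥2-fold ULN, same draw | AST/ALT | Yes, if liver enzymes includes them | No |
| | Total bilirubin | Not named | |
| Aminotransferase alone: AST/ALT ≥10-fold ULN | AST/ALT | Yes, on the same assumption | Yes |

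**Step 2: where the missing result matters.**

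| AST/ALT on the draw | Alert status without bilirubin |
|---|---|
| Below 3-fold ULN | Not met, whatever bilirubin is |
| 3-fold to below 10-fold ULN | Undetermined; depends on bilirubin |
| 10-fold ULN or above | Met, whatever bilirubin is |

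The gap is therefore the middle band.

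**Step 3: whether other rules fill it.**

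- *Symptom rule (5.2.6.1).* The investigator must have ALT, AST and total bilirubin analysed when there are clinical symptoms of hepatic injury and no results. An asymptomatic patient is outside it.
- *DILI checklist (5.2.6.1).* It follows an alert, so it cannot supply the result that decides whether there is one.
- *Repeat testing (5.2.3).* Clinically relevant abnormal results are to be confirmed with an unscheduled-visit kit and repeated. No symptoms are required, but the investigator must judge the result clinically relevant. The criterion requires values "measured in the same blood draw sample". A later bilirubin paired with the earlier ALT would not qualify. A repeat measuring both would, and the alert could be met on that repeat. This route limits the harm to delay, or to a rise that has resolved by the time of the repeat.
- *Home collection for the central laboratory (10.5).* This would supply bilirubin, but only where home visits are possible, and it does nothing for a sample tested locally.

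**Step 4: how much monitoring is exposed.** By the Flow Chart, the safety laboratory tests scheduled after baseline and up to end of treatment are at Visit 4 and (e)EoT. A minimum-panel draw at either visit loses one of two scheduled bilirubin readings. Visit 4 is the only one between first dose and end of treatment, and Section 10.5 names it among the visits that may be replaced.

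**Step 5: SAP against protocol.** The two definitions disagree only when AST/ALT is exactly 3.0-fold ULN or bilirubin exactly 2.0-fold ULN.

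**The case against.** A reader might infer that hepatic injury cannot be detected in patients followed through a local laboratory, or that the principal criterion has been lost. The documents support neither reading. The panel is both recommended and a minimum, so a local laboratory may run the full chemistry of Table 5.2.3: 1. The 10-fold criterion still works. The protocol joins the two criteria as alternatives and does not rank them. A repeat under Section 5.2.3 that measures aminotransferases and bilirubin together can itself trigger the alert.

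It is also fair to say that remote and home visits are meant for exceptional cases and need sponsor approval, and that Visit 6/(e)EoT may be delayed up to 10 days after the last dose to allow a clinic visit. Liver injury is presented in Section 1.4 as a rare possibility under general surveillance. The laboratory effect described there for this drug is a fall in hemoglobin, and hematology is in the minimum. The text available for this review lacks Section 5.2.6.2, and the DILI checklist and laboratory manual are separate documents; any of these may say more.

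These points reduce the concern to possible omission or delay. They do not remove it: a stated minimum should be sufficient for the only AESI, and the routes back to a bilirubin result depend on symptoms, on the investigator's judgement or on logistics.

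**Conclusion.** The point stands in limited form. On a draw restricted to the recommended minimum, one of the two hepatic-injury criteria cannot be assessed. An asymptomatic patient with AST or ALT from 3-fold to below 10-fold ULN may have the alert, the AESI report and the DILI checklist missed, or delayed until a repeat draw measures both analytes.

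This rests on two assumptions: that liver enzymes in Section 10.5 includes AST and ALT but not bilirubin (the term is not defined there), and that some sites test no more than the minimum. The number of patients affected cannot be estimated from the documents. Sample size and the efficacy analyses are not involved. The change is worth making because it concerns safety ascertainment and costs almost nothing. The SAP mismatch is real but minor and adds no weight.

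**What to change.** **Protocol Section 10.5.** Reconcile the minimum panel with Section 5.2.6.1 by replacing the term liver enzymes with the analytes the AESI definition already requires: AST, ALT and total bilirubin from the same blood draw. Ask for the local ULNs in the eCRF, because both criteria are multiples of ULN. Alkaline phosphatase is not needed, since neither criterion uses it.

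**SAP Section 7.8.1.** Change the two strict inequalities in the combined criterion to at-or-above, as in the definition cited.

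**Cost.** One line in the protocol, two symbols in the SAP, and one routine analyte on a tube already drawn. There is no new threshold, visit or blood draw.

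**Limit.** For a missed Visit 3, 4 or 5, Section 10.5 makes local testing subject to feasibility and the investigator's judgement. The change makes the draws that are taken assessable; it does not guarantee that a draw is taken.
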